### Safety Evaluations

A safety plan for the walking groups will be developed prior to the initiation of the study with Drs. [name] and [name], as well as the study clinicians.

### Statistical And Analytic Plan

Analyses will primarily be descriptive in nature. We will calculate means, standard deviations, and within-group effect sizes of the primary outcome (CRF) and secondary outcomes (Ioneliness, symptoms, weight, BMI, waist circumference, resting heart rate, and blood pressure). Additionally, we will examine means, standard deviations, and within-group effect sizes of intermediate targets (self-determination basic needs and autonomous motivation) and proximal outcomes (minutes spent walking and daily steps).

DATA AND SAFETY	[name] will function as the Project Medical Officer. An
MONITORING PLAN	independent physician will serve as the Medical Monitor ([name]
	[name], from the Department of Psychiatry).

### 1 BACKGROUND AND RATIONALE

Individuals with schizophrenia spectrum disorders (SSDs) have a life expectancy up to 25 years shorter than individuals in the general population primarily due to elevated levels of chronic physical and medical illnesses (1-4). Premature mortality in this population may be explained by high levels of six known modifiable risk factors for mortality: high blood pressure, smoking, raised glucose, physical inactivity, obesity, and high cholesterol (5-7), with physical inactivity and smoking being the strongest contributors to this risk (8, 9). Specifically, cardiorespiratory fitness (CRF) impacts not only cardiovascular mortality but also all-cause mortality (10-13), including in individuals with SSDs. Thus, physical inactivity contributes to significantly elevated rates of chronic medical diseases, especially cardiovascular disease (CVD) in individuals with SSDs (1, 5, 6, 14, 15). Further, despite reductions in mortality from CVD in the general population over the past 20 years, rates in people with SSDs have remained high (16, 17). Indeed, sedentary behavior and poor CRF among individuals with SSDs relative to the general population (13, 18-21) are likely major contributors to the premature mortality in this at-risk population. As a result, the potential benefits of interventions that increase physical activity (PA) in this population are substantial and could have a meaningful impact on public health.

Studies examining the effects of exercise on physical and mental health in individuals with SSDs have yielded encouraging results (22-24). Indeed, well-designed multi-component interventions that target exercise and diet, such as the ACHIEVE trial and the In SHAPE program, led to weight-loss and improved fitness in individuals with serious mental illness (25-27). However, these findings are tempered by questions of long-term accessibility and sustainability. Specifically, the In SHAPE program involved individual meetings with a trainer and continued access to a gym, perks that are inaccessible to most individuals with SSDs after study completion (26, 28-33). While a strength of the ACHIEVE trial was housing it in psychiatric rehabilitation settings, not all people with SSDs have access to such programs. In addition, attendance at the intervention sessions waned after the first 6 months of the study, which the authors attributed to hospitalizations and social issues (19) (p. 1601); however, decreasing subject motivation may have also played a role.

Prior work has been largely unsuccessful in overcoming the many barriers faced by individuals with SSDs. Specifically, exercise participation is hampered by lack of access and cost (e.g. personal trainers), biological factors such as physical health problems, social variables such as loneliness and limited social support, and self-regulatory problems (e.g., forgetting to exercise, being overwhelmed) (34-43). And, most interventions fail to address motivation, a critical factor for initiating and sustaining exercise, particularly for people with SSDs (44). Ironically, even work that has directly targeted motivation in this population (45) observed difficulties in promoting long-term adoption and sustained exercise after the program ends (46). These findings speak to the need for additional strategies to sustain motivation and ensure the effective translation of motivation into action. Thus, interventions aimed at this population should be designed and delivered in ways that address the substantial barriers to exercise, so as to promote the adoption and long-term maintenance of physical activity (47, 48).

[figure not shown]
Given the importance of motivation and translating intentions to actions, our treatment model is rooted in both self-determination theory (SDT) (49, 50) and implementation intentions (i.e., if-then plans) (51). SDT is a prominent theory of motivation which is highly suited for exercise interventions (52). SDT posits that the fulfillment of three basic psychological needs: autonomy, relatedness, and competence facilitates autonomous motivation (i.e. motivation due to one's own choice rather than as a result of external factors) (50). Autonomous motivation, in turn, is associated with levels of exercise participation in the general population (52, 53) and in people with SSDs (54).

If-then plans have the structure if (opportunity/obstacle)-then I will (response) and engender associations that mimic the effects of habits (55). If-then plans create mental links between good opportunities to act and responses that move the person towards their exercise goal (e.g., If I have to go shopping for 1-2 items, then I will walk rather than drive to the store!") or between obstacles to exercise and responses that will be effective in overcoming those obstacles (e.g., "If I am tempted not to exercise, then I remind myself how proud I feel at the end of the session!"). Two separate meta-analyses revealed that if-then plans were highly effective in increasing physical activity [ES = .31 and.38] (56, 57)] and led to sustained behavior change one year (58-61) and two years (62, 63) post-treatment. If-then plans have also demonstrated effectiveness among samples with psychiatric and clinical diagnoses (64) including people with SSDs (65). Importantly, autonomous motivation and if-then plans are known to combine synergistically, and engender better outcomes compared to the use of either strategy on its own (66, 67).

In addition to considering motivation and intention translation, we also sought to develop an exercise intervention that involves minimal staff resources, that is free and easy to access, and has the potential for long-term sustainability. Thus, we chose an intervention that requires no equipment or special training, and can be done anywhere: Walking (68, 69). Research has shown that walking leads to improved physical health, well-being, and weight loss (70-73). Furthermore, walking without dietary change has been shown to improve CRF (10, 74, 75), and reduce the risk of all-cause mortality (76), premature death (77), and the rate of cardiovascular disease (78) in the general population. Dose-response analyses have determined that the strongest health benefit accrues within the first 120 minutes per week of walking, further highlighting the potential impact of increasing PA among sedentary individuals (76). Moreover, given the widely accepted PA recommendations set forth by the American College of Sports Medicine (ACSM) (79) and by the International Organization of Physical Therapy in Mental Health (IOPTMH) (42), walking at a moderate-intensity level should be prioritized (See section C.3. for more details).

A valuable way to facilitate the initial engagement of exercise and address the barriers of social isolation in individuals with SSDs is through group-based interventions, as they promote social interaction, camaraderie, and social support (36-39, 80). Group-based interventions also impact motivation by offering the opportunity to develop friendships centered around a common goal, thus satisfying relatedness and competence needs and promoting self-efficacy (35). Walking programs in the general population that promote social support also led to greater maintenance of behavior change (81, 82). Therefore, social support (and reduction of loneliness) may play a critical role in helping individuals with SSDs initiate and adhere to exercise programs (35).

A critical component of goal setting and attainment is being able to monitor progress, which can be achieved via physical activity tracking devices. Pedometer use leads to an increase in PA – they are considered acceptable and are highly useful for setting PA goals (83-85), which helps to facilitate changes in exercise behavior (86). In fact, pedometers are the most cost-effective means of increasing PA in the general population (87). In a systematic review of 26 studies, pedometer use resulted in significant increases in PA (26.9% over baseline) (70). With recent advances in sensor and Bluetooth technologies, new physical activity monitors have emerged and are currently commercially available (e.g., Fitbit), which also allow the measuring of walking intensity (e.g., through heart rate; See Section C.3.).

The model above illustrates how our proposed intervention, (PACE-Life) will lead to increased exercise and improved outcomes. Specifically, PACE-Life includes five primary components: home-based walking, group-based walking, activity tracking, goal-setting, and if-then plans, four of which impact the SDT basic needs and one of which enhances autonomous motivation. Specifically, homebased walking targets autonomy needs (as individuals can do this independently), group-based walking targets relatedness needs, and activity tracking and goal setting target competence needs. Satisfaction of each of the SDT needs leads to the intermediate target of increased autonomous motivation. PACE-Life subjects also form if-then plans which serve to enhance the impact of autonomous motivation (66, 67) and promote actual exercise behavior (56, 57). Engaging these intermediate targets in turn engenders the proximal outcomes of greater exercise participation (as measured by minutes spent walking per week and steps/day). Finally, increased exercise should lead to the improved primary outcome of CRF as well as improved secondary outcomes of loneliness, symptoms, resting heart rate, and systolic/diastolic blood pressure.

The proposed research is highly innovative in at least three respects. First, the simplicity and practicality of PACE-life is a key innovation. As noted above, most previous interventions for individuals with SSDs required gym equipment (e.g., treadmills) as well as professional supervision to engage in exercise, thus limiting both sustainability and scalability (22-24, 26). The field demands pragmatic interventions that are low in resource costs and can be rapidly translated into clinical practice (48, 88). Our walking intervention is both cost-effective and highly accessible given that the group-based portion will be implemented in the vicinity of the outpatient clinic and the home-based portion will be completed at locations selected by subjects (e.g., outdoors on residential streets or indoors at malls during inclement weather). Additionally, the COVID-19 pandemic has provided subjects an opportunity to participate in a virtual walking intervention. Though, technological inequities may serve as a barrier to overall feasibility outside of this intervention, providing subjects with technology (e.g., tablets and data plans) has further improved potential feasibility and scalability.

Second, the focus on cardiorespiratory fitness (CRF) is novel. Although CRF has long been identified as a significant predictor of health, it has only recently received attention in exercise intervention research among individuals with SSDs. A meta-analysis on the effects of exercise on CRF in individuals with SSDs (12) revealed only 3 published randomized controlled trials that examined this health indicator (32, 89, 90). Vancampfort and colleagues (13) concluded that despite the few available studies on CRF in schizophrenia,

improvements in this domain are possible and may provide a "novel and valid exercise target that could lead to reductions in premature mortality in people with schizophrenia" (p. 456). In addition, we will measure CRF in a cost-effective and feasible manner without the need for expensive equipment, further displaying our commitment to scalability and sustainability.

Third, the present research is conceptually innovative in targeting both motivation to exercise, and the effective translation of motivation into action. Previous interventions that focused merely on generating strong intentions to exercise have had little success (91) because the quality of motivation supporting these intentions was not addressed (92). PACE-Life is deliberately designed to engender high-quality (i.e., autonomous) motivation. However, even high-quality motivation may not equip people to deal effectively with problems that are inevitably encountered as they strive to exercise. These problems include failing to get started, becoming derailed by unwanted influences (e.g., distractions), and coping badly with unforeseen obstacles and lapses (51). If-then plans are an effective tool for dealing with each of these problems experienced by new exercisers (61, 93-95) and synergize the impact of autonomous motivation, helping to turn that motivation into action.

### 2 RESEARCH DESIGN AND METHODS

### 2.1 OVERVIEW

The project will consist of three primary phases: manual development, an open trial, and a small-scale RCT (See Table 1; Table 2 indicates updated project time based on the COVID-19 pandemic). These three phases will be iterative such that we will obtain and incorporate end-user feedback from clients and clinicians. Feedback from users will inform both the open trial and subsequently, the RCT.

[figure not shown]
[figure not shown]

Table 2: Project Timeline (COVID-19 Updated)

Rationale for clinic-based/home-based rather than a gym-based exercise intervention. We propose to provide PACE-life through a mental health clinic as individuals with SSDs usually have frequent contact with their providers. Furthermore, interventions that don't require additional equipment or supervision by an exercise trainer have greater potential for integration into healthcare services for individuals with SSDs. Our rationale for a clinic-based versus a gym-based exercise program is also based upon recommendations for integrated medical care (104) as well as integrated physical activity within mental health services for this population (105). In addition to clinic-based sessions, we will include home-based sessions, which can be completed at any location and time of the subjects' choosing to improve self-management and facilitate longterm exercise adoption. The term, "home-based," means only that individuals will be engaging in this component independently and do not need to attend a select location or require additional equipment. We will work with subjects to identify convenient walking routes using websites and apps (e.g. map my walk). Therefore, our intervention will include both clinic-based sessions and instructions for home-based sessions to prioritize feasibility and sustainability. Moreover, given the disruption of the COVID-19 pandemic, we've redesigned our study to have feasibility in a virtual format. Subjects can participate in the study from their homes, as we provide them with technology (e.g., tablets and data plans) necessary for participating in virtual exercise sessions. Exercise sessions include dynamic, stationary exercises that model walking movements, to best match movements performed in outdoor walking sessions. These obstacles have provided the research team with an opportunity to learn about the sustainability and scalability of home-based virtual interventions, in addition to clinic-based interventions.

Rationale for moderate-intensity walking as exercise modality. Walking is the primary form of exercise in PACE-life given its accessibility and association with meaningful fitness and health outcomes. PACE-life will combine walking groups and Fitbit with heart rate monitoring to encourage moderate-intensity walking in individuals with SSDs. The goal of PACE-life is to facilitate engagement in 150 min/week of moderate- intensity walking spread throughout the week, which is consistent with recommended fitness guidelines set forth by the ACSM (79) and by the IOPTMH (42). To achieve this goal, we will employ a stepwise approach of exercise participation to provide individual tailoring and reduce the likelihood of dropouts (103). Specific details and rationale of this approach are discussed below:

Overview and rationale of stepwise approach. Stepwise approaches to exercise participation are often recommended for use with sedentary populations to reduce the risk of injury and dropouts (32, 103). Typically, these interventions will begin at low intensity and low frequency, and as individuals become more physically active, the intensity and frequency increase. This strategy is especially relevant to individuals with SSDs as they are quite sedentary and have little experience with consistent participation in exercise. Furthermore, individuals need to engage in moderate-intensity exercise, defined as exercising within 60-70% of heart rate reserve (HRR), in order to achieve meaningful changes in CRF (103). In sedentary individuals, moderate to high intensity exercise may not be achievable immediately in the first weeks of the program and starting physically deconditioned individuals in a program that is too intense can be physically dangerous and lead to significant dropouts (103, 106). As a result, a step-wise approach that begins at a lower-intensity and increases to moderate intensity is more appropriate and has been successfully implemented in SSDs (32, 89). For the present study, low and moderate intensity exercise will be operationalized by HRR (103, 106) where Low-intensity Exercise = 50-60% of HRR and Moderate-intensity exercise = 60-70% of HRR.

We ([name], PI) demonstrated the potential benefits of a step-wise exercise program in African-American breast cancer survivors that began at a low intensity and later progressed to moderate intensity (107). The results showed a high completion rate (76%) and adherence to walking goals (70%).

### 2.2 SUBJECTS

Based on the grave health concerns, physical inactivity, and growing urgent calls for action in individuals with psychotic disorders (116, 117), 56 study subjects will be recruited from various clinics in the Durham, Carrboro, Chapel Hill, and Raleigh area including, the UNC Schizophrenia Treatment and Evaluation Program (STEP) clinic in Raleigh and Carrboro, the Outreach and Support Intervention Services (OASIS) program in Chapel Hill, Carolina Behavioral Care, Club Nova, and Threshold. All subjects will have a primary diagnosis of a schizophrenia spectrum disorder. To obtain an estimate of IQ and to rule out any individuals with possible mental retardation, we will administer the WASI, which is comprised of Matrix Reasoning, Vocabulary, Similarities, and the Block Design subtests. During the COVID-19 pandemic, we will also administer the WRAT to test the reading level of participants. Additional demographic and clinical information that will be collected as self-report for possible use as covariates includes: 1) demographics: age, sex, ancestry, education, parent education; 2) health: smoking, substance use, current medications, duration of outpatient treatment, diet, physical activity, height, weight, BMI, and waist and hip circumference.

### 2.2.1 INCLUSION CRITERIA

- 1. DSM-V diagnosis of a Schizophrenia Spectrum Disorder (Schizophrenia, Schizoaffective Disorder, Brief Psychotic Disorder, Schizophreniform Disorder, and Unspecified Schizophrenia Spectrum and Other Psychotic Disorder)
- 2. Age 18 or above, both genders, and any ancestry
- 3. IQ>70; Reading Level > 4th Grade
- 4. No hospitalizations in the last 3 months
- 5. Clinically stable (no medication changes within the past month)
- 6. Are not already engaging in consistent moderate-intensity exercise (cutoff = 60 min/week for the past 6 months)
- 7. Present with no contra-indication to engage in regular moderate intensity exercise based on the ACSM guidelines (118). If individuals answer yes to one or more items on the of the PAR-Q, a questionnaire that assesses cardiovascular risk factors, she/he will require further evaluation by a physician prior to participating in the study
- 8. Willing and able to provide informed consent.

### 2.2.2 EXCLUSION CRITERIA

1. Pregnant women will be excluded because pregnancy alters autonomic and immune responsiveness, increase weight gain, and can influence heart rate.

### 3 ASSESSMENT OF DATA

At this stage of treatment development, specific outcomes include:

- 1. Feasibility (Can PACE-life be delivered within this treatment setting?)
  - Will determine if recruitment procedures yield the target number of subjects in 3 months
  - Will determine feasibility of assessments based on subject compliance rates
- 2. Tolerability (How well is PACE-life accepted by the subjects?)

- Will be evaluated by examining subject attendance to groups, adherence to homebased component of program, Fitbit usage, and dropout rates.
- 3. Intervention adherence
- 4. Evaluation of PACE-life. We will evaluate feasibility in two ways. First, we will determine if recruitment procedures yield the target number of subjects in 3 months. Second, we will determine feasibility of assessments based on subject compliance rates. The tolerability of PACE-life will be evaluated by examining subject attendance to groups, adherence to homebased component of program, Fitbit usage, and dropout rates.

### 3.1 OUTCOMES

The central hypothesis is that an intervention that increases physical activity as measured by minutes spent walking (at the prescribed intensity) and steps/day will result in improved health and lowered risk for premature mortality as evidenced by superior CRF (primary outcome), and on a variety of secondary outcomes (e.g. blood pressure). Guided by strong preliminary data and grounded in SDT, this hypothesis will be tested via three specific aims:

- 1. To develop a manual-based walking intervention for individuals with SSDs: PACE-Life. The manual will include guidelines for goal setting and translating intentions into behaviors (i.e., "if-then" plans), instructions for the group-based walking activity and home-based walking activity (which includes Fitbits), and increasing exercise intensity in a step-wise manner.
- 2. To examine the feasibility of implementing PACE-life at a community mental health clinic, and in a home-based virtual capacity, in a randomized controlled trial of 56 individuals with SSDs.
- 3. We will also examine the impact of PACE-life on intermediate targets (autonomous motivation and SDT needs), proximal outcomes (minutes spent walking and steps/day), the primary outcome of CRF, and secondary outcomes.

We hypothesize that PACE-life will be associated with:

- Improved proximal and primary outcomes including greater minutes/week spent walking and steps/day and increased CRF at mid-treatment (3 months), post-test (6 months), and one-month follow-up;
- Decreases in secondary outcomes including loneliness, SSD symptoms, resting heart rate, and blood pressure at mid-point, post-test, and one-month follow-up.
- Higher levels of theoretically-relevant, intermediate targets (autonomous motivation and SDT needs) at mid-treatment, post-test, and one-month follow-up.

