### 4.2.2 BASELINE, MID-POINT, POST-TEST, 1 MONTH FOLLOW-UP

The following measures will be examined at the baseline, mid-point, post-test, and 1 month follow-up study visits:

- Demographics- We will collect information on age, sex, ancestry, education, parent education, smoking, substance use, current medications, duration of outpatient treatment, and diet.
- Minutes Spent Walking- We will utilize data recorded from Fitbits to assess minutes spent
  walking (by syncing Fitbits to corresponding Fitbit.com accounts and loading deidentified data
  onto study laptops).

- The Short Form International Physical Activity Questionnaire (IPAQ), a valid self-report
  measure, to assess changes in physical activity. The IPAQ Short Form is a four-item scale that
  assesses frequency and duration of walking, moderate-intensity exercise, vigorous-activity
  exercise, and sitting.
- Steps/day. We will also collect daily step numbers using Fitbit data downloaded onto study laptops from Fitbit.com at group sessions.
- Cardiorespiratory fitness (CRF)- CRF will be measured using the 6-minute walk test (6MWT) during which individuals are asked to walk continuously for six minutes on a flat, indoor surface around cones (separated by 100ft) and the primary outcome is the total distance walked. The 6MWT is recommended for use with sedentary individuals and to evaluate the impact of an exercise intervention. Moreover, the 6MWT has been successfully administered to individuals with SSDs, including those in our pilot trial. As a result, we plan to utilize the 6MWT as our primary measure of CRF. Supplemental CRF measures will also be used. CRF will be calculated using an equation by Jackson, A. S., et al. 1990 (119) that includes recent weight and height for the calculation of BMI, gender, self-reported physical activity level, and age. Finally, participants will complete a Chair-Rise Task, where subjects will sit and stand from a chair for 30 seconds, and the 2-minute Step Test, where subjects will walk in place with their knees raising to hipheight, to measure CRF.

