### **5.2 POWER ANALYSIS**

Power was estimated using Optimal Design Software. Assuming n=56 (28 per group), alpha=05, and the covariate accounted for 50% of variance, the proposed study has reasonable power to detect an effect size of .50 or larger in comparison of the groups at the end of treatment or follow-up and of .75 or larger in comparisons of the size of change over time. Thus, this study has good power to detect the types of differences detected in pilot study (ES of .50-1.03 in steps, .33-.40 in six-minute walk test, .54-.83 for BP and .52-1.09 for symptoms).

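### No primary visit or contrast is named for the 6MWT: 3.1 claims CRF benefit at three visits, 5.2 powers single comparisons, and 5.1 plans within-group description

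*Combined protocol and SAP*

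**What the plan says.** Section 3.1 sets out a central hypothesis of superior CRF, labels CRF the primary outcome, and states that "this hypothesis will be tested via three specific aims". It then lists the expected benefit as "increased CRF at mid-treatment (3 months), post-test (6 months), and one-month follow-up". The three visits are joined by 'and', and none is singled out.

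Section 4.2.2 fixes the measure: for the 6MWT, "the primary outcome is the total distance walked". It attaches no visit to that statement, and neither does the efficacy paragraph of the synopsis.

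Section 5.2 makes two power statements from the same inputs. The first is "reasonable power to detect an effect size of .50 or larger in comparison of the groups at the end of treatment or follow-up". The second is "of .75 or larger in comparisons of the size of change over time". Mid-treatment does not appear in 5.2, no power percentage is given, and no adjustment for multiple comparisons is mentioned.

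Section 5.1 and the statistical paragraph of the synopsis describe the analysis as mainly descriptive: means, standard deviations and within-group effect sizes. Section 5.1 adds the percentage of participants with a clinically significant 6MWT change. Neither place gives a between-group test, a significance level, a success rule or a visit.

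**The concern.** The three sections answer different questions. Section 3.1 claims an effect at three visits. Section 5.2 supports one between-group comparison at either of two visits, or a different contrast on change. Section 5.1 plans summaries within each arm, which do not compare the arms at all. A reader cannot tell which number will be the trial's answer on its primary outcome.

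The first cost is selection. With several candidate visits and contrasts and no ranking, the one to emphasise could be settled after the data are in. This matters more here because participants know whether they attend walking groups, walking distance depends on effort, and the sections reviewed describe no masked assessment.

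The second cost arises only if the hypothesis is tested, as 3.1 says. The operating characteristics then depend on an unstated rule. If all three visits must succeed, power is lower than for one comparison. If any visit is enough, the false-positive rate exceeds 5%.

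**Working it through.** **Inputs from 5.2.** "Assuming n=56 (28 per group"), alpha read as .05, and "the covariate accounted for 50% of variance", so R² = .50. The effect size is in units of the unadjusted standard deviation.

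**Assumptions, not in the documents.** Two-sided test; no dropout; the same true effect at each visit; correlation of the baseline-adjusted test statistics across visits of .3 to .9.

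**Step 1: the plan's own figures, one comparison.**
- Standard error of the adjusted difference = sqrt((1 − .50) × 2/28) = .189.
- Noncentrality at .50 = .50/.189 = 2.65. Degrees of freedom = 56 − 3 = 53; two-sided critical value 2.006.
- Power = 73.8% (75.4% by the normal approximation).
- Effect detectable with 80% power = (1.960 + .842) × .189 = .53.

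So the .50 statement is roughly right for exactly one comparison. The .75 statement matches a comparison without the covariate: standard error sqrt(2/28) = .267, detectable effect (1.960 + .842) × .267 = .75, power 80.1% (78.7% by the t distribution).

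**Step 2: three visits.** Three correlated t statistics with 53 degrees of freedom were simulated. The any-visit columns have no true effect at any visit; the all-visits column has a true effect of .50 at each.

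| Correlation between visits | Any of 3 significant: false positives | All 3 significant: power | Any of 2 significant: false positives |
|---|---|---|---|
| .3 | 13.6% | 47% | 9.5% |
| .5 | 12.7% | 52% | 9.1% |
| .7 | 11.1% | 57% | 8.3% |
| .8 | 9.8% | 61% | 7.8% |
| .9 | 8.6% | 65% | 7.1% |

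For reference, three independent tests give 1 − .95³ = 14.3% and two give 1 − .95² = 9.75%. The last column covers the two visits that 5.2 names.

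**Step 3: the two consequences are alternatives.** Requiring all three visits does not raise the false-positive rate above 5%; it only lowers power from about 74% to 47-65%. Accepting any visit does not lower power; it raises the false-positive rate from 5% to about 8-14%. A plan that names one comparison has neither problem.

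**Step 4: the date of post-test.** Section 3.1 places mid-treatment at 3 months and post-test at 6 months. Section 4 gives a 16-week intervention, and the synopsis gives 4 months of intervention plus a 1-month follow-up. The in-person schedule in 4.1 runs to week 24 and the virtual schedule to week 16. As written, post-test does not have one calendar date.

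**The case against.** The strongest reply is that 5.1 and the synopsis plan a mainly descriptive analysis with no test and no success rule. An error rate needs a decision rule, and the documents contain none. The objectives also put feasibility, tolerability and adherence first. This stands as far as it goes: the error and power figures are conditional on testing. It does not remove the gap, because 3.1 says the hypothesis will be tested and 5.2 gives an alpha, group comparisons and a claim of good power. Even a purely descriptive report needs its headline visit and contrast fixed in advance.

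Three stronger readings are tempting and are not supported.

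- *The trial's type I error is inflated.* A reader might infer this from the 'or' in "in comparison of the groups at the end of treatment or follow-up". The natural reading is that the same detectable effect applies at either visit because the sample size is the same. It is not a rule that success at either visit is enough. The 'and' in 3.1, taken literally, leaves the error rate at or below 5%.
- *The power stated in 5.2 is wrong.* Section 5.2 states no percentage, and its .50 figure is reasonable for one comparison. It also offers the .75 change-over-time contrast; had that been named as the single primary contrast, the multiplicity would not arise. No section names it.
- *Power for all three visits collapses because the effect at mid-point is small.* The stepwise schedule in 4.1 makes a smaller early effect plausible, but the documents give no figure for it, so no calculation here relies on one.

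**Conclusion.** The gap is real: no section names the primary visit or the primary contrast for 6MWT distance, and 3.1, 5.1 and 5.2 point to different analyses. The certain consequence is that the headline result is left open until after the data are seen.

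The numerical consequence is conditional on testing at two-sided .05 with 28 per arm, R² = .50 and no dropout. Section 5.2 then fits one comparison only, with about 74% power at .50. Requiring all three visits gives about 47-65%; accepting any of three gives about 8-14% false positives. These ranges rest on the assumed correlation of .3-.9, and the power range also on an equal effect of .50 at every visit. The documents do not support a claim that error is inflated in the analysis as currently described. This is a cheap improvement to the plan.

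**What to change.** - In 3.1, 5.1, 5.2 and the synopsis, name one primary comparison: the PACE-Life minus Fitbit-only difference in 6MWT distance at post-test, adjusted for baseline distance, with a 95% CI. Changing only 3.1 and 5.2 would leave 5.1 and the synopsis without the between-group analysis.
- Present mid-point and one-month follow-up as supportive between-group estimates with 95% CIs and no claim of success.
- In 5.2, state that the .50 figure applies to that single comparison.
- If only description is intended, keep this between-group estimate as the headline and remove the testing and power claims from 3.1 and 5.2.
- Reconcile the 6-month label for post-test in 3.1 with the 16-week and 4-month durations in section 4 and the synopsis, and with the two schedules in 4.1, so that the primary visit has one date.

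The cost is a few sentences in four places and no new data, since the 6MWT is already planned at every one of these visits. The small downside is that a result at mid-point or follow-up alone can no longer be presented as the primary result.
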